## 1.0 Background

Left ventricular assist device (LVAD) patients remain at risk for pump thrombus and thromboembolic events through multiple mechanisms. The HeartWare® Ventricular Assist System (HVAD®, HeartWare Inc., Framingham, MA, USA) includes a novel speed modulation feature called Lavare™ cycle. It consists of 3 phases: phase 1 – a 200 rpm decrease from baseline speed for 2 seconds, phase 2 – a 100 rpm increase from baseline for 1 second and phase 3 – return of speed to baseline; this cycle repeats itself once every minute. The Lavare™ Cycle is aimed to promote washing of left ventricle to decrease blood stasis and subsequent risk of thrombus formation, ingestion and/or expulsion. In a post-hoc analysis of ReVOLVE registry, which includes 248 patients implanted with the HVAD following Conformité Européenne Mark in nine centers in Europe and Australia, no adverse impact on survival was observed with Lavare™ cycle. Additionally, lower risk of stroke, sepsis and right heart failure was observed among those with Lavare™ cycle in the abovementioned study. However, no prior study has prospectively evaluated the impact of Lavare™ cycle on patient outcomes in a randomized fashion.

## 2.0 Rationale and Specific Aims

**Primary objective:** To assess feasibility of conducting a future larger trial that investigates whether, among patients receiving HeartWare LVAD, Lavare cycle results in lower risk of pump-related complications.

### Outcomes of interest:

#### 1. Primary

- a. Composite endpoint of total ischemic events, thrombotic or thromboembolic events/Pump Hemolysis/Pump Thrombosis/ Pump exchange

#### 2. Secondary

- a. All-cause mortality
- b. Survival to transplantation
- c. LVAD related complications
  - i. Stroke
  - ii. Transient ischemic attack
  - iii. Mucocutaneous bleeding
  - iv. Right ventricular failure
  - v. Infection: LVAD system related
  - vi. Moderate or Severe aortic insufficiency
- d. Changes in biomarkers

- e. Re-hospitalizations
- f. Echocardiographic changes in myocardial structure and function
- g. Functional status
  - i. NYHA functional class
  - ii. 6-minute walk test
- h. Quality of life
  - i. KCCQ

**Design:** This is a pilot 2-arm prospective randomized controlled trial. Both treatment strategies, Lavare cycle on and off, are consistent with standard of care.

**Study Population:** This trial will enroll patients undergoing their first HeartWare LVAD implantation as well as those chronically supported with HeartWare LVAD. Clinical data will be collected at baseline and at regular post-enrollment follow-up until trial ends. For chronically supported patients, minimum support duration of 3-months will be required.

**Duration of follow-up:** 180-days; follow-up visits will be logged at 30-days, 90-days and 180-days.

### 3.0 Inclusion/Exclusion Criteria

#### Inclusion Criteria:

1. Age  $\geq$ 18 years
2. Approved for or supported with HeartWare durable left ventricular assist device
3. Capable of giving informed consent

#### Exclusion Criteria:

##### 1. New implantation:

[figure not shown]
- a. Age  $<$ 18 years
- b. INTERMACS profile 1 at the time of implantation
- c. Presence of intra-cardiac thrombus
- d. History of thromboembolic event within previous 3 months of enrollment
- e. Chronic Kidney disease stage 4 or 5, or on any form of dialysis (eGFR must be consistently documented  $<$ 30 for 30 days)

**2. Previous HeartWare implant with active support:**

- a. Support duration <3 months
- b. History of prior LVAD pump exchange
- c. History of LVAD pump hemolysis or thrombosis as defined by INTERMACS criteria
- d. History of stroke or transient ischemic event within previous 3 months of enrollment
- e. History of post-LVAD severe right ventricular failure as defined by INTERMACS criteria within previous 3 months of enrollment
- f. History of pump-related infection treated within previous 3 months of enrollment or those on chronic antibiotics suppressive therapy for pump related infection
- g. History of post-LVAD intra-cardiac or arterial thrombus or thromboembolic event within previous 3 months of enrollment
- h. INR <2 within previous 30-days from the date of enrollment
- i. Aspirin dose <325 mg/day
- j. LDH levels  $\geq$  3 times the upper normal limit in previous 3 months
- k. Chronic kidney disease stage 4 or 5, or any form of dialysis (eGFR must be consistently documented <30 for 30 days).

#### 4.0 Enrollment/Randomization

**Number of subjects:** N=100; 50 patients undergoing their first HeartWare LVAD implantation and 50 patients with chronic HeartWare LVAD support will be included. This multi-center study will be conducted at up to 4 sites.

#### Procedures for randomization

Using REDCap, participants will be randomly assigned in a 1:1 ratio. Participants will receive a randomization number. The randomization number identifies the participant for all procedures occurring after randomization. Once a randomization number is assigned to a participant, it cannot be re-assigned to another participant.

There are 2 arms:

- 1) LavareTM Cycle - On  
**OR**
- 2) LavareTM Cycle – Off

## 5.0 Study Procedures

Screening Visit: Visit 1 (prior to new LVAD implantation for New Implants and at the time of consent for Previous Implants)

- Informed Consent
- Demographics
- Review of Medical History
- Blood sampling for biomarkers (approximately 20mLs)
- KCCQ questionnaire
- 6-minute walk test (Can be deferred if patient is on inotropic or MCS support)
- NYHA functional class assessment defined as follows:
  1. Class I - No symptoms and no limitation in ordinary physical activity, e.g. shortness of breath when walking, climbing stairs etc.
  2. Class II - Mild symptoms (mild shortness of breath and/or angina) and slight limitation during ordinary activity.
  3. Class III - Marked limitation in activity due to symptoms, even during less-than-ordinary activity, e.g. walking short distances (20-100 m). Comfortable only at rest.
  4. Class IV - Severe limitations. Experiences symptoms even while at rest. Mostly bedbound patients.
  5. No NYHA class listed or unable to determine.

Data will be collected on the following tests that were likely performed as part of the standard LVAD evaluation. The participant will not be required to undergo these tests for the purposes of this trial:

- Echocardiogram
- Right heart catheterization or Swan-Ganz Catheterization

The Screening Visit and the Randomization Visit can occur on the same day, if all study criteria have been met.

The following will happen:

- Randomization: Randomly assigned by REDCap to one of the two groups:  
1Lavare™ Cycle - On  
**OR**  
2 Lavare™ Cycle – Off
- Study intervention: Changes in Lavare™ Cycle will be made by the study staff according to the group you are assigned.
- LVAD data: standard parameters displayed on the screen upon routine interrogation of the LVAD will be collected.

**Visit 2: Day 30 (+/- 14 Days)**

- Review of Medical History
- Blood sampling for biomarkers
- 6-minute walk test (Can be deferred if patient is on inotropic or MCSD support)
- NYHA functional class assessment defined as follows:
  1. Class I - No symptoms and no limitation in ordinary physical activity, e.g. shortness of breath when walking, climbing stairs etc.
  2. Class II - Mild symptoms (mild shortness of breath and/or angina) and slight limitation during ordinary activity.
  3. Class III - Marked limitation in activity due to symptoms, even during less-than-ordinary activity, e.g. walking short distances (20-100 m). Comfortable only at rest.
  4. Class IV - Severe limitations. Experiences symptoms even while at rest. Mostly bedbound patients.
  5. No NYHA class listed or unable to determine.
- LVAD data: Standard parameters displayed on the screen upon routine interrogation of the LVAD will be collected. We will also ask Medtronic to provide trends in the LVAD parameters over past 30 days utilizing log-files that are stored in their data bank. **Please send log-files to Medtronic with a title: Lavare Trial Log-Files for appropriate storage and analysis.**
- Adverse Events

Data will be collected on the following tests that were likely performed as part of the standard LVAD evaluation. The participant will not be required to undergo these tests for the purposes of this trial:

- Echocardiogram
- Right heart catheterization or Swan-Ganz Catheterization

**Visit 3: Day 90 (+/- 14 Days)**

- Review of Medical History
- Blood sampling for biomarkers (approximately 20 mLs)
- KCCQ questionnaire
- 6-minute walk test (Can be deferred if patient is on inotropic or MCSD support)
- NYHA functional class assessment defined as follows:
  1. Class I - No symptoms and no limitation in ordinary physical activity, e.g. shortness of breath when walking, climbing stairs etc.
  2. Class II - Mild symptoms (mild shortness of breath and/or angina) and slight limitation during ordinary activity.
  3. Class III - Marked limitation in activity due to symptoms, even during less-than-ordinary activity, e.g. walking short distances (20-100 m). Comfortable only at rest.
  4. Class IV - Severe limitations. Experiences symptoms even while at rest. Mostly bedbound patients.
  5. No NYHA class listed or unable to determine.

- LVAD data: Standard parameters displayed on the screen upon routine interrogation of the LVAD will be collected. We will also ask Medtronic to provide trends in the LVAD parameters over past 30 days utilizing log-files that are stored in their data bank. **Please send log-files to Medtronic with a title: Lavare Trial Log-Files for appropriate storage and analysis.**
- Adverse events

Data will be collected on the following tests that were likely performed as part of the standard LVAD evaluation. The participant will not be required to undergo these tests for the purposes of this trial:

- Echocardiogram
- Right heart catheterization or Swan-Ganz Catheterization

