Functional parameters	6-minute walk test, NYHA functional class	X	X	X	X
Echocardiogram		X	X	X	X
Review of Medical History		X	X	X	X
Pulmonary artery catheter data		X	X	X	X
VAD specific variables	Implantation indication (DT/BTT), Implant Technique (sternotomy/ thoracotomy), INTERMACS class, Inotropes (presence, types and duration), Temporary support device (presence, type and duration), diuretics (types, doses)	X			
VAD parameters	(power, PI, flow, speed, hematocrit), log-files	X	X	X	X
Quality of life	KCCQ score	X		X	X
Post Implant VAD related AE's	Arterial and venous thromboembolic events, neurological dysfunction, bleeding, pump hemolysis/thrombosis/exchange, pump malfunction, myocardial infarction, infection, right heart failure, aortic regurgitation, re-hospitalizations, cardiac arrhythmia, hypertension, major renal, respiratory or hepatic dysfunction and other major adverse events.		X	X	X

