### **11.0 Statistical analysis**

Statistical analysis will be performed using software STATA version 13 (StataCorp, College Station, TX). Baseline characteristics will be compared using Wilcoxon-Rank Sum test for continuous variables and Fisher's exact test for categorical variables. Multivariable regression analyses will be performed to assess for risk of primary and secondary outcomes with Lavare cycle on and off. Changes in laboratory parameters, echocardiographic measures, functional status and quality of life will be assessed using multivariable regression analyses. Statistical significance will be defined as  $p<0.05$ .

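### Nothing in the plan keeps the assigned Lavare setting from participants or functional raters, so an arm difference in KCCQ, NYHA class or 6-minute walk could reflect expectation

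*Combined protocol and SAP*

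**What the plan says.** The Design paragraph in Section 2.0 reads "This is a pilot 2-arm prospective randomized controlled trial" and uses neither an open-label nor a blinded label. It adds that both settings are consistent with standard of care. Section 4.0 gives the allocation, "Using REDCap, participants will be randomly assigned in a 1:1 ratio", and the sample, "50 patients undergoing their first HeartWare LVAD implantation and 50 patients with chronic HeartWare LVAD support will be included".

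Section 5.0 says how the intervention is delivered: "Changes in Lavare™ Cycle will be made by the study staff according to the group you are assigned". Each follow-up visit then lists the 6-minute walk, NYHA class and a device check, with KCCQ added at day 90 and day 180. The device item reads "LVAD data: Standard parameters displayed on the screen upon routine interrogation of the LVAD will be collected", and the Schedule of Events gives the recorded items as ("power, PI, flow, speed, hematocrit), log-files".

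For the analysis, Section 11.0 says "Changes in laboratory parameters, echocardiographic measures, functional status and quality of life will be assessed using multivariable regression analyses", with significance at p<0.05.

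**The concern.** KCCQ is a self-report, NYHA class is a judgement of symptoms, and walk distance depends partly on effort. Each can shift if the participant or the rater knows the arm and expects something from it. The protocol supplies grounds for expectation: Section 1.0 describes a feature meant to wash the ventricle and cites registry data with lower stroke risk, while Section 6.0 raises hypothetical suction events and low-flow alarms with the cycle on.

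The intervention also looks easier to mask than most device comparisons. It is a controller setting that, by Section 1.0, involves "a 200 rpm decrease from baseline speed for 2 seconds" and a 100 rpm increase for 1 second, once a minute. The documents give no reason for not attempting to mask it.

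What is at stake is the reading of three secondary outcomes. The pilot's stated purpose is to assess the feasibility of a larger trial. Whether participants can be kept unaware of the setting is information that trial would need, and it cannot be recovered after the pilot ends. The point does not concern classification of the primary composite events.

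**Working it through.** **Reading check.** The supplied text was read for any provision on masking, concealment of the setting, visit order or separate assessors.

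- Section 2.0 (Design): no statement on masking.
- Section 4.0 (randomization): 1:1 assignment through REDCap; silent on whether the participant is told the arm.
- Section 5.0, screening and randomization: study staff make the change, so at least some staff know the arm. Screening and randomization may fall on the same day, with no rule that baseline KCCQ, walk and NYHA come before the assignment is known.
- Section 5.0, days 30, 90 and 180: walk, NYHA and interrogation share every visit; KCCQ joins them at days 90 and 180 only. The bullets list the functional items before the device item, but a bullet list does not require an order.
- Section 9.0: data that would reveal treatment may be added after clean file. This is a database step. It suggests that some masking was in mind, but no procedure elsewhere provides it.
- Section 11.0: no provision for knowledge of assignment.
- Section 12.0: masking refers to names and initials on copied documents.

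**Illustration of size.** The plan has no power calculation, SD or bias figure, so there is nothing of its own to reproduce.

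From the documents: N = 100 at 1:1, so n = 50 per arm; alpha = 0.05. Assumed: two-sided test (sidedness is not stated), no true Lavare effect, an expectation shift of 3 or 5 KCCQ points between arms, SD of 20 or 25, complete data, and an unadjusted two-sample t-test.

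With d = shift/SD, the noncentrality is d × √(n/2) = d × √25 = 5d. The rejection probability is P(|T| > t₀.₉₇₅,₉₈), where T is noncentral t with 98 degrees of freedom and the critical value is 1.984.

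| Shift / SD | d | 5d | P(p<0.05) with no true effect |
|---|---|---|---|
| 3 / 25 | 0.12 | 0.60 | 0.091 |
| 3 / 20 | 0.15 | 0.75 | 0.115 |
| 5 / 25 | 0.20 | 1.00 | 0.168 |
| 5 / 20 | 0.25 | 1.25 | 0.236 |

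The normal approximation, 1 − Φ(1.96 − 5d) + Φ(−1.96 − 5d), gives 0.170 at d = 0.20, in agreement. Within one 50-patient group (25 per arm), the same assumptions give 0.070 to 0.139.

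**The case against.** The strongest objection is that the route to bias is inferred. A reader might conclude that interrogation shows the rater the Lavare status, or that participants are told their arm. The documents say neither. The recorded screen items do not include Lavare status, and the consent pages, which would largely govern what participants are told, are not in the supplied text. This stands. What remains is that staff who set the cycle know the arm, and nothing in the retained procedures stops them from rating function or discussing the setting.

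Second, visit order cannot mask someone who set the device at randomization. This also stands, and is why a separate rater belongs in the fix.

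Third, it is tempting to repeat the comparisons without participants who learned their setting. That selects on a post-randomization event. People with more clinical contact or more complications could be removed, possibly unequally by arm, so the check could add bias. It should not be done.

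Fourth, a reader might infer that Section 11.0 presents these as unbiased comparisons, or that a functional signal will be carried into the larger trial. Section 11.0 specifies only regression and a significance level, and the stated objective for the larger trial concerns pump-related complications.

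Fifth, the percentages show only that some bias inflates error. They ignore missing KCCQ data from death or transplantation, do not model the planned multivariable regression, and say nothing about NYHA or the walk. That is correct, so they serve as an illustration and not as an estimate.

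**Conclusion.** The point holds as a modest improvement to conduct. No supplied text keeps the setting from participants or functional raters, and three judgement- or effort-dependent secondary outcomes are tested without allowing for this. An arm difference in them could therefore reflect expectation. Neither the size nor the direction can be derived from the documents: the background favours the cycle on, while the risk section could work the other way. The 9% to 24% range rests wholly on the assumed shift and SD, with 50 complete observations per arm. A masking statement on the removed title or consent pages cannot be excluded, but no procedure in the body would carry it out.

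The documents do not support saying that these outcomes are biased. They support saying that the plan leaves open a risk it could reduce at little cost.

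**What to change.** 1. In Section 4.0 and the randomization part of Section 5.0, state that participants are not told their assigned setting and that the treating LVAD team keeps full access to it for care.
2. At every visit in Section 5.0, including baseline, require KCCQ (where collected) to be self-completed first, then the walk and NYHA, all before the device is interrogated or its setting is changed or discussed.
3. Where existing staffing allows, have NYHA and the walk done by someone who did not set the device.
4. At day 180, ask which setting the participant believes they had, and report the answers by arm.
5. Reconcile the database wording in Section 9.0 with the actual masking status, and state that status in the Design paragraph.
6. In Section 11.0, keep all randomised participants in the KCCQ, NYHA and walk comparisons, and state that these outcomes are interpreted as only partially masked.

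The cost is consent and visit-order wording plus one question at day 180, with no additional procedures. Item 3 depends on staff already available. The downside is that masking will be partial: some participants, especially the 50 who are chronically supported, may know or learn their setting through routine care.

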#### **Visit 4: Day 180 (+/- 30 Days)**

- Review of Medical History
- Blood sampling for biomarkers (approximately 20 mLs)
- KCCQ questionnaire
- 6-minute walk test (Can be deferred if patient is on inotropic or MCS support)
- NYHA functional class assessment defined as follows:
  1. Class I - No symptoms and no limitation in ordinary physical activity, e.g. shortness of breath when walking, climbing stairs etc.
  2. Class II - Mild symptoms (mild shortness of breath and/or angina) and slight limitation during ordinary activity.
  3. Class III - Marked limitation in activity due to symptoms, even during less-than-ordinary activity, e.g. walking short distances (20-100 m). Comfortable only at rest.
  4. Class IV - Severe limitations. Experiences symptoms even while at rest. Mostly bedbound patients.
  5. No NYHA class listed or unable to determine.
- LVAD data: Standard parameters displayed on the screen upon routine interrogation of the LVAD will be collected. We will also ask Medtronic to provide trends in the LVAD parameters over past 30 days utilizing log-files that are stored in their data bank. **Please send log-files to Medtronic with a title: Lavare Trial Log-Files for appropriate storage and analysis.**
- Adverse events

Data will be collected on the following tests that were likely performed as part of the standard LVAD evaluation. The participant will not be required to undergo these tests for the purposes of this trial:

- Echocardiogram
- Right heart catheterization or Swan-Ganz Catheterization

Schedule of Events		At the time of randomization	30-day Visit (+/- 14 days)	90-day Visit (+/- 14 days)	180-day Visit (+/- 30 days)
Demographics	Age, gender, race	X			
Comorbidities	Etiology of heart failure, Atrial arrhythmia, Ventricular arrhythmia, Hypertension, Diabetes, Hyperlipidemia, Cerebrovascular event Peripheral arterial disease, Cancer, Chronic kidney disease and its stage, Dialysis, COPD, Obesity, Presence of pacemakers/ ICD (BiV/ dual/ single), Prior cardiac surgery, History of sternotomy, Number of sternotomies, History of hypercoagulable disease, History of prior DVT, History of prior PE, History of HIT	X			
Laboratory values	Basic chemistry panel, Complete blood count with differential, Liver function test, INR, LDH, Urine analysis	X	X	X	X
Biomarkers	NT-pro-BNP, ST-2, GDF-15, Galactin-3, Hs-CRP, TNF-alpha, IL-6, NGAL, KIM-1, TIMP-2, IGFBP-7, Ang-2, Ang-1, Soluble Tie-2, VEGF, Thrombin, vWF,	X	X	X	X
Functional parameters	6-minute walk test, NYHA functional class	X	X	X	X
Echocardiogram		X	X	X	X
Review of Medical History		X	X	X	X
Pulmonary artery catheter data		X	X	X	X
VAD specific variables	Implantation indication (DT/BTT), Implant Technique (sternotomy/ thoracotomy), INTERMACS class, Inotropes (presence, types and duration), Temporary support device (presence, type and duration), diuretics (types, doses)	X			
VAD parameters	(power, PI, flow, speed, hematocrit), log-files	X	X	X	X
Quality of life	KCCQ score	X		X	X
Post Implant VAD related AE's	Arterial and venous thromboembolic events, neurological dysfunction, bleeding, pump hemolysis/thrombosis/exchange, pump malfunction, myocardial infarction, infection, right heart failure, aortic regurgitation, re-hospitalizations, cardiac arrhythmia, hypertension, major renal, respiratory or hepatic dysfunction and other major adverse events.		X	X	X

## 6.0 Risks

We do not have data to detail potential risks and their chances arising from participation in this study. This study aims at understanding this very question.

Hypothetically, conditions that lead to decreased blood volume in the left side of the heart (such as dehydration, excessive bleeding, right HF, fluid around the heart, etcetera) can increase the chances of suction events or low flow alarms with implementation of the Lavare™ Cycle.

1. Suction event occurs when decreased blood volume in the left side of heart causes part of left heart wall *sucked over* the LVAD pump's inflow cannula; the result of this event is reduction in LVAD pump speed to reduce the suction pressure and free up the sucked over left heart wall.
2. Low flow alarm is triggered when average flow through the pump drops below the set limit.

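### Suction events and low-flow alarms, the only harms Section 6.0 names for the Lavare Cycle, have no recording prompt and no planned by-arm summary

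*Combined protocol and SAP*

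**What the plan says.** **Risks (Section 6.0).** The protocol states that it has no data to detail "potential risks and their chances arising from participation in this study. This study aims at understanding this very question". It then says that, hypothetically, conditions reducing blood volume in the left heart "can increase the chances of suction events or low flow alarms with implementation of the Lavare™ Cycle". No other harm is named; bleeding, dehydration, right heart failure and pericardial fluid appear only as predisposing conditions. The alarm depends on a setting: "Low flow alarm is triggered when average flow through the pump drops below the set limit".

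**Outcomes (Section 2.0).** The primary composite covers ischemic, thrombotic and thromboembolic events, pump hemolysis, pump thrombosis and pump exchange. Secondary item (c), on LVAD complications, is a list of six: stroke, TIA, mucocutaneous bleeding, right ventricular failure, device infection and aortic insufficiency. Neither Section 6.0 event is among them.

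**Adverse events (Section 5.0, Schedule of Events).** The row covers thromboembolic events and then, among others, "neurological dysfunction, bleeding, pump hemolysis/thrombosis/exchange, pump malfunction, myocardial infarction, infection, right heart failure". It ends with "respiratory or hepatic dysfunction and other major adverse events". Suction and low flow are not named.

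**Device data (Section 5.0).** At Visits 2, 3 and 4 the on-screen parameters are collected and the manufacturer is asked to "provide trends in the LVAD parameters over past 30 days utilizing log-files". A separate instruction tells sites to send log-files to the manufacturer for storage and analysis, with no time span. The Schedule lists the VAD parameters as ("power, PI, flow, speed, hematocrit), log-files".

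**Analysis (Section 11.0).** Multivariable regression is planned for the primary and secondary outcomes and for changes in laboratory, echocardiographic, functional and quality-of-life measures. VAD parameters, log-files and adverse events outside the outcome list are not mentioned.

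**The concern.** The plan states a risk-related aim, names two events that bear on it, and then sets up no assured way of counting them. Bleeding, infection and neurological events each have a named place on the adverse-event row; these two do not. A suction episode or low-flow alarm that a site regards as routine may never be written down, and a table added at the end cannot recover what was not recorded or requested.

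What is at stake is descriptive safety information. The primary objective is to judge whether a larger trial is feasible. A per-arm count of the device events thought plausible with the cycle on would help that trial plan its safety monitoring, and as written the pilot need not produce one.

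**Working it through.** The plan gives no figure on this point, so there is nothing to reproduce. The check has two parts.

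**1. Is there any route from event to by-arm result?**

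| Place in the plan | Could it capture these events? | By-arm result planned? |
|---|---|---|
| Section 2.0, primary and secondary outcomes | Not listed | No |
| Schedule, adverse-event row | Only if a site uses pump malfunction or the catch-all for major events | No |
| Section 7.0, SAE reporting through REDCap | Yes, if the episode meets an SAE criterion such as hospitalization | No |
| Visits 2-4 adverse-event item, with Section 9.0 data entry | Yes, if the investigator judges it an adverse event | No |
| VAD parameters and manufacturer trends | Flow and speed are listed; suction and alarm entries and the low-flow limit are not | No |
| Log-files sent by sites | Unknown; content not stated | No; the analysis is not described |

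Every possible route depends on site judgement or on unstated file content, and none ends in a planned comparison or table.

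**2. How much of follow-up does the trend request reach?**

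Inputs from Section 5.0: look-back of 30 days; visits at day 30 (±14), day 90 (±14) and day 180 (±30).

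- On schedule: days 1-30, 61-90 and 151-180, so 30 + 30 + 30 = 90 days, and 90/180 = 50%. Trends are not requested for days 31-60 and 91-150 (30 + 60 = 90 days).
- Lowest share over the permitted visit days, counting follow-up to the actual Visit 4: visits at days 16, 76 and 210 give 16 + 30 + 30 = 76 days, and 76/210 = 36.2%.
- Highest share: visits at days 44, 104 and 150 give 90 days, and 90/150 = 60.0%.
- Counting only days 1-180, the range is 46 to 90 days. The low end again has visits at days 16, 76 and 210: 16 + 30 + 0 = 46.

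The Schedule also marks log-files at randomization, but a look-back from that point adds no follow-up days.

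If each request reached back to the previous visit, on-schedule coverage would be 30 + 60 + 90 = 180 of 180 days, provided the files hold that much.

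**The case against.** Four objections deserve a hearing.

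**The log-files may hold more than the trends.** This stands. The 30-day limit applies to the trends asked of the manufacturer. Log-files are a separate collected item with no stated span. A reader might infer that days 31-60 and 91-150 go unobserved. The documents do not support that; they show only that trends are not requested for those days. Equally, they do not say that the files contain suction or alarm entries.

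**Non-serious events can reach the central database.** This stands in part. Section 7.0 keeps adverse events in site records, and a reader might infer that non-serious episodes never leave the site. But adverse events are an unrestricted item at Visits 2-4, and Section 9.0 has site staff enter protocol-specified observations into REDCap. So there is a possible central route. What is missing is a prompt and a planned summary.

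**The harms are hypothetical and partly covered.** Section 6.0 uses that qualifier, and a low-flow alarm is a device signal rather than an injury. Serious episodes can be reported as SAEs, and right ventricular failure and re-hospitalization are secondary outcomes compared by arm. This limits the weight of the point but does not supply a count of the two events.

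**Bias from partial coverage is speculative.** A reader might infer that event proportions will be understated. With a constant event rate and half of follow-up seen, the observed proportion is 1 − (1 − p)^0.5, so an assumed 40% versus 20% over 180 days would appear as 22.5% versus 10.6%. But the plan gives no event rates and no such analysis, and the formula also assumes that the files record these events. A rate ratio per observed day would not be biased if coverage were equal by arm. The illustration shows why days covered should be recorded; it is not evidence of a flaw in a planned result.

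**Conclusion.** The point holds in limited form. The plan names two possible harms of the cycle and says it aims to understand risk, yet it neither prompts for these events nor commits to reporting them by arm. The only size the documents support is the trend request: 90 of 180 days on schedule, and 36.2% to 60.0% of follow-up across the permitted visit days. How many events would be missed cannot be estimated, because event rates, log-file span and log-file content are not given.

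The efficacy comparisons in Section 11.0 are untouched, and nothing here suggests that patients are at unmonitored serious risk, since SAE reporting applies whether or not a causal link is suspected. This is a minor, inexpensive improvement, best made before data collection because unrequested entries may not be recoverable later.

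**What to change.** 1. **Schedule of Events.** Name suction events and low-flow alarms in the adverse-event row. Record the set low-flow limit with the VAD parameters, since alarm counts cannot be interpreted without it.
2. **Visits 2-4.** Replace the 30-day look-back with: *since the previous visit (at Visit 2, since randomization or implantation, whichever is later), including suction and low-flow alarm entries where the file holds them*. Record the days each file covers.
3. **Section 11.0.** Add a descriptive safety line: *Suction events and low-flow alarms will be reported by arm as patients with at least one event and as events per 30 log-file days observed, with 95% confidence intervals allowing for repeat events within a patient and without significance tests.* Keep this outside secondary item (c) of Section 2.0. Listed there, the events would fall under Section 11.0's regression and its 0.05 significance threshold, contrary to the descriptive intent.

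**Cost.** A longer data request to the manufacturer and some work to summarize entries by patient. No visit, blood test or significance test is added. If files hold only 30 days, full coverage would need extra downloads between visits; reporting per observed day avoids that expense, with less precision.
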